- *Cigarette littering message (Control)*: Messages about littering cigarettes will include text designed to discourage people from littering their cigarette butts, and an image related to the message. Each condition has 5 messages that will be repeated 3 times in a counterbalanced order. Study investigators used text developed by

investigators associated with our Center for Regulatory Research on Tobacco Communication. Design of these messages was developed by our team.

Randomization

At the end of the baseline survey, survey software will randomly assign participants to one of the three study arms. Participants will have an equal chance of being randomized to each study arm.

Sample Size

Sample Size Background:

Our study is examining the difference in quit intention for participants that receive 1) Optimal constituent messages with quitline information, and self-efficacy information, or 2) Sub-optimal constituent messages or 3) Messages about littering cigarette butts.

[figure not shown]
No studies from the literature that we could find examined difference in quit intention or quitting behaviors by optimal text vs. sub-optimal warning text vs. control in a warning or smoking communication context.

In a meta-analysis by Noar et al. 2014 (Pictorial cigarette pack warnings: a meta-analysis of experimental studies) the effect size between pictorial vs. text only warnings on intention to quit smoking was $d=0.54$. Other outcomes ranged between effect size $d=-0.03$ (recall of warning text), and $d=1.82$ (intention not to start smoking).

Assumptions for the power calculation:

- The smallest effect size between our groups will be between the optimal and sub-optimal group. If we can see a difference between these groups, we will be able to see the larger effects that we expect between the other groups.
- We will be using a continuous measure of quit intention (or treating quit intention as a continuous variable, and collecting it as a categorical response).
- The effect size on quit intention is likely to be smaller for added self efficacy and quit line text than for added pictorial images.
- To be conservative, we will use a one time measure to calculate power, repeated measures would add power to this analysis (decrease necessary sample size).
- We will use the d statistic to see what group size would have to be enrolled, and compare two means (optimal and sub-optimal) with a t-test

Based on these assumptions:

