- Adherence for the daily surveys will be presented with completion % as well as the mean number complete by treatment group
- Completion of post test surveys will be presented by % completing each by treatment group

Definition of protocol deviations for the trial

- Minor protocol deviation: change in eligibility (ex: turning 66) between screening and baseline
- Minor protocol deviation: completing the wrong sequence of message days due to survey signal error
- Major protocol deviation: No protocol deviations in this trial will impact the safety or physical or mental integrity of the participants in the trial. A slightly older participant, or a participant that receives a slightly different number of messages will both be included as covariates during analysis, so they will not impact the scientific validity of the trial. Therefore, we do not classify any protocol deviations as 'major'

Description of which protocol deviations will be summarized

- Protocol deviations will not be summarized overall, but data related to the deviations will be included in manuscripts. For example, we will not say X participants were older than 65, but will include mean age in a demographic table by treatment group. Similarly, we will not include how many people completed an extra 'day' of the protocol, but we will report the mean number of days participants completed by treatment group.

Analysis Populations

Definition of analysis populations

Outcomes assessed only at post test (including quit intentions) will be analyzed using multiple imputation such that everyone who was randomized will be included in the analysis, and those with missing outcome data will have their outcomes imputed.

For outcomes that were measured daily, all participants that completed at least one of the daily surveys will be included in the planned repeated measure models.

Secondary outcomes may be analyzed using complete case analysis, without imputation.

Trial Population

Screening Data

Screening data will be provided based on the CONSORT guidelines, and CONSORT flow chart will be included with publications.

Eligibility

Minimum Age: 18 Years

Maximum Age: 65 Years

Sex: All

Gender Based: No

Inclusion Criteria:

[figure not shown]
- Have smoked at least 100 cigarettes in his or her lifetime
- Currently smoke cigarettes every day or some days
- Work or home access to the internet
- Email account that is regularly used
- Lives in the US
- Comfortable taking a survey in English

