- Able to complete a survey on a computer
- Able to complete surveys delivered via email
- Able to complete 3, 20 minute surveys during the study
- Able to complete surveys in the morning for 15 days

Exclusion Criteria:

- Currently using pharmacotherapy, a quitline, or a quit smoking program or support group for smoking cessation
- Participated in a research study about smoking cigarettes or using other tobacco products in the last 3 months

Recruitment

Recruitment data will be provided based on the CONSORT guidelines. The following CONSORT chart will be used as a template for reporting recruitment.

Withdrawal/follow-up

Level of withdrawal

- Data collection and the intervention occur using the same surveys, when a participant withdraws from data collection, they are withdrawing from follow up and the intervention.

Timing of withdrawal/lost to follow-up data

- Timing of withdrawal will be presented by treatment group, and categorized into each of the following timepoints:
 - o After baseline but before beginning intervention (before completing first daily survey)
 - o During intervention (days 1-15)
 - o During post-test follow up period (days 16-32)
 - o After post-test follow up period (after day 32)

Reasons and details of how withdrawal/lost to follow-up data will be presented

- Numbers (with reasons) of loss to follow up and withdrawal over the course of the trial will be summarized by treatment group

Baseline participant characteristics

List of baseline characteristics to be summarized

See Draft Table 1 below.

Details of how baseline characteristics will be descriptively summarized

Baseline characteristics will be descriptively summarized as show in Draft Table 1.S

Draft Table 1. Baseline Sample Characteristics

Sample Characteristics	Condition 1 (n=XXX)		Condition 2 (n=XXX)		Condition 3 (n=XXX)		Total Sample (n=XXX)	
	% or mean	95% CI	% or mean	95% CI	% or mean	95% CI	% or mean	95% CI
Gender								
Male								
Female								
Age, years								
Race								
White								
Black or African American								
Other Race								
Ethnicity								
Latino/Hispanic								
Non-Latino/Hispanic								
Education								
<High School (HS)								
G12 or GED, HS Diploma								
Some College								

Associate's degree								
Bachelor's degree								
Graduate or professional degree								
Poverty Status								
Below Poverty Line								
Above Poverty Line								
Sexual Orientation								
Straight or heterosexual								

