What analysis method will be used and how treatment effects will be presented

Linear regression for continuous outcomes, logistic for dichotomous.

Any adjustment for covariates

Covariates included for the imputation (in addition to treatment group):

- Dose of ads (# of times participants viewed a message)
- Gender (Male, Female, Other) (The GenIUSS Group, 2014)
- Age (continuous)
- Poverty Status (Above or Below Poverty Line)(Brewer et al., 2018; Department of Health and Human Services, 2017)
- Education (6 categories, same as phone survey)
- FTND Sum Using scoring from Heatherton et al. 1991 (Fagerstrom Test for Nicotine Dependence)(Fagerstrom, Heatherton, & Kozlowski, 1990; Heatherton et al., 1991)

Covariates included in the analysis model (in addition to treatment group):

- Dose of ads (# of times participants viewed a message)

Methods used for assumptions to be checked for statistical methods

For continuous outcomes, we assume the distribution of dependent variable given a predictor variable (intervention) is 1) independent 2) normality 3) constant variance (homogeneity of variance). We can check normality with Q-Q plot of the residual or perform Wilk-Shapiro test and use a scatter plot of residual on predictor variable (intervention) to check independence and constant variance.

Details of alternative methods to be used if distributional assumptions do not hold (eg normality, proportional hazards, etc)

If we have a violation for normality assumption, we can have two options: 1) transform our data so that the shape of our response variable become normally distributed or 2) choose the non-parametric method like Kruskal-Wallis which does not require the assumption of normality. The ANOVA can be considered a robust test against the normality assumption though. If the assumption of homogeneity of variances has been violated, we can use Welch or Brown and Forsythe test. Even though we alternatively perform a Kruskal-Wallis test, in most cases, Welch test is best. We don't expect to have dependency issues in our data.

Any planned sensitivity analyses for each outcome where applicable

Sensitivity analyses may be carried out using a 'complete case analysis' framework

Any planned subgroup analyses for each outcome including how subgroups are defined

None a priori

Missing Data

Multiple imputation will be used so that everyone who was randomized to an intervention will be included in the primary analysis

Additional Analyses

None a priori

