Construct (Source)	Question Text	Response Option	Pretest Var Name	Post 1 Var Name	Post 2 Var Name
Quality Assurance	Would you recommend this study to a friend?	0=No 1=Yes		QA5	
Quality Assurance	Did anything annoy you, if so, what?	[text box]		QA6	
Quality Assurance	Is there anything that you would like to share about your experience in the study?	[text box]		QA7	
Quality Assurance	Did you have any difficulty remembering how many cigarettes you smoked? If yes, please explain.	[text box]		QA8	
Quality Assurance	Would you have preferred to receive the surveys for this study via text message?	0=No 1=Yes		QA9	
PAGE BREAK					
Instructions for Enrolling in Survey Signal	
On the next page, you will be redirected to a new link (SurveySignal). It is very important that you fill out the information on that page (including name, email address, etc.). If you do not fill out that information, you will NOT be enrolled in the study. If you have any questions, email [contact].
 
Once you fill in your information, SurveySignal will send you an email to verify your email address. Please make sure that you verify your email, so that you will be enrolled in the study.
 
Note: If you are using a Mac, you will need to open the link in Chrome or Firefox.
		SurveySignal_Inst		
End of Survey for anyone that is no longer a	Unfortunately you are no longer eligible for our study. We will send you a check for \$20 to compensate you for your time completing this survey, but you will not be able to complete the rest of the study.				

Construct (Source)	Question Text	Response Option	Pretest Var Name	Post 1 Var Name	Post 2 Var Name
smoker (smoke_stat_ pre =0)	Thank you for taking the time to complete this survey!				

Morning Questionnaire (to be answered between 7am – 11am every morning)

Construct (Source)	Question Text	Response Option	Var Name
Study ID	[Auto-recorded]	numerical	
Behavior Instructions	Please think about yesterday		Behav_Inst
	What time did you wake up yesterday?	Time	Time#1_Wake_Hour
	What time did you go to sleep last night?	Time	Time#1_Sleep_Hour Time#2_Wake_Min Time#2_Sleep_Min Time#3_Wake_AMPM Time#3_Sleep_AMPM
Behavior ⁴	How many times yesterday did you dispose of your cigarette butts by dropping them on the ground?	Dropdown list 0-100, 101=refused	Lit1
	How many times yesterday did you dispose of your cigarette butts by throwing them or dropping them out of the car window?		Lit2

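### Randomisation appears to come before the registration step that lets participants receive messages, and the listed imputation then gives people who saw no message the arm difference of people who did

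*Combined protocol and SAP*

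**What the plan says.** On timing, the protocol (Allocation and Blinding) and the SAP (Randomization) agree: "At the end of the baseline survey, survey software will randomly assign participants to one of the three study arms". Neither names the software.

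In Appendix A, the row on enrolling in SurveySignal carries a pretest variable name, so it belongs to the baseline instrument. It sends the participant to a new link to enter personal details and says: "If you do not fill out that information, you will NOT be enrolled in the study". SurveySignal then sends an e-mail, and the participant is told: "Please make sure that you verify your email, so that you will be enrolled in the study". The SAP's list of protocol deviations ties the same system to delivery, naming as one deviation "completing the wrong sequence of message days due to survey signal error".

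On the primary analysis, the SAP (Analysis Populations) says that "everyone who was randomized will be included in the analysis, and those with missing outcome data will have their outcomes imputed", and its Missing Data entry for post-test measures repeats: "Multiple imputation will be used so that everyone who was randomized to an intervention will be included in the primary analysis". The imputation terms listed there are treatment group, dose (number of messages viewed), gender, age, poverty status, education and nicotine dependence. The analysis model has treatment group and dose. No arm-by-dose term appears in either list. The only sensitivity analysis mentioned is a complete-case one, and it is optional.

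The SAP expects some early loss. One withdrawal category, to be shown by treatment group, is "After baseline but before beginning intervention (before completing first daily survey").

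**The concern.** Messages are shown only inside the morning surveys, and the post-test surveys are the same for every arm. A person who is randomised but never completes SurveySignal registration therefore meets nothing specific to the arm. Between arms, the true difference among such people is zero. They also have no day-16 quit intention, so the primary analysis must impute one.

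The imputation model learns the arm difference only from people with outcomes, who are people who registered. If arm and dose enter as separate terms, setting dose to zero shifts every arm by the same amount and leaves the arm difference intact. The result is labelled as the effect in everyone randomised, but in substance it is the effect among those who registered. What is at stake is the size of the reported effect. The excess is proportional to the effect itself, so this mechanism produces no difference where the messages have none.

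**Working it through.** **Inputs.** Effect d = 0.25 between the two constituent arms, 253 per group, 80% power, 759 in total (SAP, Sample Size). Alpha 0.05 (SAP, Confidence Intervals and P Values). Equal allocation (SAP, Randomization). Model terms from the SAP's covariate lists for post-test measures. Assumed here: two-sided testing, SD of 1, and u, the share of those randomised who never register, from 2% to 20%.

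**The plan's own figure.** A two-sided t-test at 0.05 with 80% power for d = 0.25 needs 252.13 per group, which rounds up to 253, and 3 × 253 = 759. The figure reproduces. A one-sided calculation gives 198 and does not fit. The value 0.25 is used below as δ, the effect in people who receive messages.

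**Order of events on the natural reading.** (1) Baseline questions. (2) Arm assigned at the end of the baseline survey. (3) Redirect to the SurveySignal form. (4) Verification e-mail. (5) First morning survey and first message. Step 4 cannot fall inside the baseline survey, because the e-mail is sent only after the form is filled in. Someone who stops between steps 2 and 5 without registering has an arm, a dose of 0 and no day-16 outcome.

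**Effect in everyone randomised.** (1-u) × δ + u × 0 = (1-u)δ.

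**What the listed imputation returns.** With main effects only, the imputed mean is a + b(arm) + c × dose + covariates. At any fixed dose, including 0, optimal minus sub-optimal is b(optimal) - b(sub-optimal), which is estimated in registrants and equals δ on average. The analysed difference is then (1-u)δ + uδ = δ. The excess is uδ and the ratio to the true all-randomised effect is 1/(1-u).

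| u (assumed) | True effect, (1-u) × 0.25 | Listed imputation | Ratio | Overstatement |
|---|---|---|---|---|
| 2% | 0.245 | 0.25 | 1.020 | 2% |
| 5% | 0.2375 | 0.25 | 1.053 | 5% |
| 10% | 0.225 | 0.25 | 1.111 | 11% |
| 20% | 0.200 | 0.25 | 1.250 | 25% |

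**Simulation check.** 800 people were randomised with equal probability to three arms. Registrants viewed on average 15 × 0.8 = 12 messages. Arm means in the exposed were 0 (control), 0.25 (sub-optimal) and 0.50 (optimal), with no effect in non-registrants. A further 5% of registrants had missing outcomes. Ten imputations used arm and dose, the analysis used arm and dose, and there were 1,500 runs per row. The other listed covariates were left out; entered as main effects, they do not alter the arm difference at dose 0.

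| u | Mean estimate after imputation | Mean all-randomised difference, full data |
|---|---|---|
| 0 | 0.253 | 0.253 |
| 5% | 0.252 | 0.240 |
| 10% | 0.247 | 0.223 |
| 20% | 0.255 | 0.201 |

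The Monte Carlo standard error of the estimates is about 0.0025. The imputed estimate stays near 0.25 while the all-randomised effect falls, as the algebra says.

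**The case against.** The strongest objection is that the order is inferred. The allocation software is not named, and SurveySignal could itself allocate after registration. Appendix A has no row for randomisation, and its row order is not a reliable flow chart: the exit page for people who no longer smoke is listed after the SurveySignal row. This stands, and the point is conditional on it. Even so, allocation at the end of the baseline survey, with verification by a later e-mail, most naturally puts allocation first.

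Second, keeping everyone randomised is good practice. Agreed; the difficulty lies in the values imputed for people with no exposure, not in their inclusion.

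Third, the SAP lists covariates without giving the functional form, and an arm-by-dose term would change the result. That is true, but no such term is listed, so an analyst following the list would fit main effects.

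Fourth, part of this is already covered. Losses before the first daily survey are to be reported by arm with reasons, and a CONSORT chart is promised. This makes such losses visible but leaves the imputation unchanged. The optional complete-case analysis looks only at people with outcomes, so it does not recover the all-randomised effect either.

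Last, u is unknown. If it is about 2%, the overstatement is also about 2% and matters little.

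**Conclusion.** The concern holds conditionally. If allocation precedes registration and verification, and imputation uses the listed terms as main effects, the all-randomised effect is overstated by a factor of about 1/(1-u): 2% at u = 2%, rising to 25% at u = 20%. The range is assumed, because the documents give no registration rate. The figures also rest on a zero arm difference among people who receive no message.

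Three stronger readings are tempting and are not supported:

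- *That non-registrants use up part of the 800 and cost power.* The SAP's sample size section counts people enrolled, and Appendix A says non-registrants are not enrolled. If the word means the same in both places, this loss is zero.
- *That the plan has two conflicting denominators.* The Appendix A text is an instruction to participants and defines no analysis set. The SAP defines the primary set once and repeats it consistently. What is missing is a statement linking randomised and enrolled.
- *That non-verified people should simply be dropped from the analysis.* The estimate would stay at about 0.25. A post-randomisation exclusion would only relabel it as the effect in registrants, without recovering the all-randomised effect.

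**What to change.** Amend the protocol (Allocation and Blinding) and the SAP (Randomization) so that the arm is assigned only once SurveySignal registration and e-mail verification are complete, and name the software that does it. This removes this group of zero-exposure randomised participants at the cost of one change in survey flow.

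That may no longer be possible. The SAP is dated July 24, 2018 and cites a final dataset whose file name carries the previous day's date, which suggests, without stating it, that data collection was over. If allocation has already taken place before verification:

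- keep everyone randomised in the primary analysis;
- amend the SAP's imputation entry for post-test measures so that participants who viewed no message are imputed with no arm difference, for example by control-based imputation, as the primary analysis or at least as a pre-specified sensitivity analysis;
- show non-verified participants by arm in the CONSORT chart.

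With no arm difference imputed for non-registrants, the target becomes (1-u) × 0.25 + u × 0, which is the all-randomised effect. The cost is a slightly smaller reported effect or a little more analysis work.
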